7.3 Objection by minors

In the study, participants will be asked to provide a blood sample. Drawing blood is an invasive procedure, it is considered a non-therapeutic intervention by the CCMO. Prior to asking the participant to consent to the study, we will discuss with the parents/legal guardian(s) if the minor objects to the procedure. Due to the extra difficulties in obtaining blood from children, mainly due to bad accessibility of veins and needle fear, blood samples will be obtained during routine clinical visits when blood collection is already planned. If the participant shows any signs of refusal to cooperate, the procedure will be stopped immediately. To determine what actions would constitute refusal to cooperate in minors, we will use the "Code of Conduct regarding Refusal by Minors Participating in Medical Research "Gedragscode bij verzet van minderjarigen die deelnemen aan medischwetenschappelijk onderzoek" (website CCMO).

7.4 Benefits and risks assessments, group relatedness

One general aim of this study is to describe the general health status of the Dutch haemophilia population. Haemophilia is a congenital disease and is therefore present from birth. To accurately capture the burden of disease in all haemophilia patients, one must also include minors in this study.

Another general aim of this study is to identify novel determinants of inhibitor formation, joint bleeding and joint damage. The distribution and incidence of many determinants differ greatly between younger and older patients and are more prevalent in younger patients. Also, to be of

58

clinical use, any determinant for inhibitor formation or joint damage should be detectable at as young an age as possible, this will allow clinicians to modify each patient's individual therapy so as to avoid inhibitor formation or excessive joint damage. Therefore, research on novel determinants of inhibitor formation, joint bleeding and joint damage cannot be performed accurately without including minors in the study.

Health-related quality life and quality of care will also be assessed in this study. Using only adults to evaluate health-related quality life and quality of care will yield results that are not applicable to minors. Therefore, minors will have to be included if the results of this research are to be applicable to minors.

The risks associated with venepuncture are minimal. The most common complication is the formation of a haematoma near the venepuncture site. Another common complication is a vasovagal response during or shortly after venepuncture which can result in dizziness or loss of consciousness, nausea, tinnitus and/or profuse sweating. Needle fear is common among PWH, however, most PWH will be very familiar with venepuncture, as PWH are used to receiving regular intravenous infusions. In addition, we will be drawing blood from all minors and most adults during routine blood collection moments. Therefore, the burden associated with venepuncture will be minimal.

The risk of bleeding associated with a FVIII wash-out phase of three days for haemophilia A patients and a FIX wash-out phase of five days for haemophilia B patients is minimal. All studies that aim to measure baseline FVIII/FIX levels require such a washout phase, there is no mention of a significantly increased risk of bleeding in the literature as a result of this washout phase. Given the half-life of FVIII and FIX, the increase in bleeding risk is predicted to be minimal.

7.5 Compensation for injury

The sponsor/investigator has a liability insurance which is in accordance with article 7 of the WMO. The sponsor also has an insurance which is in accordance with the legal requirements in the Netherlands (Article 7 WMO). This insurance provides cover for damage to research subjects through injury or death caused by the study. The insurance applies to the damage that becomes apparent during the study or within 4 years after the end of the study.

7.6 Incentives

Individuals that participated in all previous HiN studies will receive a HiN-6 mug. Also, 20 prizes for a gift card (with a value of \leq 30 each) will be drawn. Participants will also receive a detailed report of the most important findings that have resulted from the study.

Chapter 8 - Administrative aspects, monitoring and publishing

8.1 Handling and storage of data and documents

For each study participant, personal identifiers will be replaced with a unique study code using an encryption key.

Patient information will be extracted from each participant's medical record using a case report form (CRF). All CRFs will be sent to the coordinating centre where the data will be transferred into a database, this data will not contain any personal identifiers. Participants in the study will use their unique study code to gain access to the digital questionnaire. The questionnaire software and the resulting dataset will not contain personal identifiers. All blood/DNA/urine samples will be labelled with the participants unique study code, the labels will not contain any personal identifiers.

The researchers will only have access to the de-identified dataset. Only a data manager not involved in the research project will have access to the encryption key of the existing dataset. Patient data together with patient material will be stored indefinitely in the biobank.

Individual patients will not be identified within resulting publications or presentations from the study. Data will be held and processed by the study coordinator. All data will be held securely. Individual patients will not be identified within resulting publications or presentations from the study. The handling of personal data will comply with the Dutch Personal Data Protection Act (in Dutch: De Wet Bescherming Persoonsgegevens, Wbp).

8.2 Monitoring and Quality Assurance

This study requires low-intensity monitoring due to its low risk (see form 'Risicoclassificatie klinisch onderzoek'). Validation checks of clinical data will be performed by the study team. Data stored at the coordinating centre will be checked for missing or unusual values (range checks) and consistency.

8.3 Amendments

Amendments are changes made to the research after a favourable opinion by the accredited METC has been given. All amendments will be notified to the METC that gave a favourable opinion.

8.4 Annual progress report

The sponsor/investigator will submit a summary of the progress of the study to the accredited Medical Research Ethics Committee (METC) once a year. Information will be provided on the date of inclusion of the first subject, numbers of subjects included and numbers of subjects that have completed the study, serious adverse events/ serious adverse reactions, other problems, and amendments.

8.5 Temporary halt and (prematurely) end of study report

The investigator/sponsor will notify the accredited METC of the end of the study within a period of 8 weeks. The end of the study is defined as the last patient's last visit. The sponsor will notify the METC immediately of a temporary halt of the study, including the reason of such an action. In case the study is ended prematurely, the sponsor will notify the accredited METC within 15 days, including the reasons for the premature termination. Within one year after the end of the study, the investigator/sponsor will submit a final study report with the results of the study, including any publications/abstracts of the study, to the accredited METC.

8.6 Public disclosure and publication policy

The results from different centres will be analysed in close collaboration with participating centres and will published as soon as possible. Depending on the research question, one or more of the participating centres will take the lead in analysing and publishing the results. Each centre will have the right to use data collected at the centre itself. There are no restrictions for the publication of the results from the study.

8.7 Authorship

Results generated by the processing of all collected data will be published under the name of all investigators. According to the ICMJE (International Committee of Medical Journal Editors) guidelines authors should meet the following three conditions 1) substantial contributions to conception and design, or acquisition of data, or analysis and interpretation of data; 2) drafting the article or revising it critically for important intellectual content; and 3) final approval of the version to be published.

Appendix 1: Case Report form

PATIENT IDENTIFIER |__|_|_|_|_|

MONTH AND YEAR OF BIRTH |__| / |__| / |__| (mm/yyyy)

CENTRE _____

CRF FILLED IN BY _____

1.0 Diagnosis

1.1 Vital status	O Alive	
	O Deceased, date of death:	dd/mm/yyyy
	(continue below)	
	O cause of death:	
	O Cause of death unknown	
1.2 Type of haemophilia	O Haemophilia A	
	O Haemophilia B	
	O Haemophilia B Leyden	
	O Unknown	
1.3 Ethnic origin	O Caucasian	
	O Black African	
	O Asian	
	O Mixed	
	O Unknown	
	O Other:	
1.4 ABO Blood group	ΟΑ	
	OB	
	O AB	
	00	
	O Unknown	

1.5 F8 or F9 genotype known	O No (continue with question 1.6) O Yes (fill in below):		
1.5.1 Specific F8 or F9 genotype	O F8 genotype: intron 22 inversion O Other F8 genotype: O F9 genotype:		
1.5.2 Please note the nomenclature used to specify F8 or F9 genotype	O HAMSTeRS/HADB nomenclature ('old' numbering) O HGVS nomenclature ('new' numbering) O Unknown		
1.6 Baseline FVIII/FIX:C (one-stage clotting assay)	O : IU/mL, Date: O Unknown	_dd/mm/yyyy	
1.7 Baseline FVIII/FIX:C (chromogenic assay)	O : IU/mL, Date: O Unknown	_dd/mm/yyyy	
1.8 Baseline FVIII/FIX:C (two-stage clotting assay)	O : IU/mL, Date: O Unknown	_dd/mm/yyyy	
1.9 Baseline FVIII/FIX antigen	O : IU/mL, Date: O Unknown	_dd/mm/yyyy	
1.10 Baseline Von Willebrand activi	ty		
(using VWF:Rco assay)	O VWF:Rco assay was used: IU/mL, Date: O Unknown, (continue below):	_dd/mm/yyyy	
	Was a different VWF activity assay used? O Yes, namely: assay Result: (unit of measurement: Date: dd/mm/yyyy O Unknown)	
1.11 Von Willebrand antigen	O Result: IU/mL Date: dd/mm/yyyy O Unknown		

1.12 Does the patient also have	O No
Von Willebrand disease (VWD)?	O Yes (select only one option):
O VWD Type 1	O VWD Type 2, no further subtyping
O VWD Type 2A	O VWD Type 2B
O VWD Type 2M	O VWD Type 2N
O VWD Type 2 Vicenza	O VWD Type 3
O VWD Type unknown	O Other type of Von Willebrand disease:
1.13 Does the patient also have a	0 No
platelet function disorder?	O Yes (select only one option):
O Glanzmann's thrombasthenia	O Bernard-Soulier Syndrome
O (Delta) storage pool disease	O Gray platelet syndrome
O Platelet disorder: type unknown	O Other platelet disorder:
1.14 Does the patient also have an	O No
additional clotting factor	O Yes (select only one option):
deficiency?	
O Factor I (Fibrinogen) deficiency	O Afibrinogenemia
O Hypofibrinogenemia	O Hypodysfibrinogenemia
O Dysfibrinogenemia	O Factor II (Prothrombin) deficiency
O Factor V deficiency (Parahaemop	hilia) O Combined factor V+VIII deficiency
O Factor VII deficiency	O Factor X deficiency
O Factor XI deficiency (Haemophilia	C) O Factor XIII deficiency
O Combined factor II+VII+IX+X defic	iency O Alfa-2-antiplasmin deficiency
O Factor deficiency type unknown	
O Factor deficiency: type unknown	O Other factor deficiency:
O Factor denciency: type unknown	O Other factor deficiency:

2.0 Current treatment

2.1 Cumulative numl	per of exposure	2			
days (EDs) to FVIII or	FIX to date	O < 50 EDs			
		O 51-100 EDs			
		O 101-150 ED	S		
		O > 150 EDs			
		O unknown			
2.2 Age at first joint	bleed	0 :	mm/	′уу	
		O Unknown			
2.3 Is the patient cur (FEIBA or rFVIIa)?	rently on prop	hylaxis with FV	/III/FIX produc	ts or bypassing	therapy
		O Unknown			
		O No (patient	is treated on-o	lemand)	
		O Yes (fill in b	elow)		
2.3.1 Product used (s	elect only one	product):			
O Factor VIII product	S				
O Aafact	O Advate	O Adynovate	O Afstyla	O Alprolix	O BeneFIX
O Elocta	O Haemate P	O Helixate Ne	xGen	O Iblias	O Idelvion
O Immunine	O Kogenate	O Kovaltry	O Mononine	O Nanotiv	O Nonafact
O NovoEight	O Nuwiq	O Octanate	O Refacto AF	FuseNGo	O Rixubis
O Other:	O Unknown				
O Factor IX products					
O Alprolix		O Idelvion	O Immunine	O Mononine	O Nonafact
O Rixubis	O Other:	O Unknown			
O Bypassing agents:					
O FEIBA	O rFVIIa	O Other:	O Unknown		
O Unknown					
Note additional infor	mation				
for this product:		O Dose:		O IU/kg	O U/kg
				Ο μg/kg	O Other:
		Frequency:	times per	O day	O 2 days
				O 3 days	O 1 week
				O 2 weeks	O Other:
		O Unknown			

2.4 Treatment protocol

2.4.1 Treatment of a minor bleed?

O DDAVP O Factor VIII product	S				
O Aafact O Elocta O Immunine	O Advate O Haemate P O Kogenate	O Kovaltry	xGen O Mononine		O BeneFIX O Idelvion O Nonafact
O NovoEight O Other:	O Nuwiq O Unknown	O Octanate	O Refacto AF	FuseNGO	O Rixubis
O Factor IX products O Alprolix O Rixubis	O BenefIX O Other:	O Idelvion O Unknown	O Immunine	O Mononine	O Nonafact
O Rixubis O Bypassing agents: O FEIBA	O rFVIIa	O Other:			
O Unknown	OTFVIId	0 Other			
Note additional infor for selected product:		O Dose:		Ο IU/kg Ο μg/kg Ο U Ο Other:	Ο U/kg Ο IU Ο μg
		O Unknown			
2.4.2 Treatment of a	major bleed?				
O Factor VIII product O Aafact	s O Advate	0 Advnovate	O Afstyla	O Alprolix	O BeneFIX
O Elocta	O Haemate P	•	•	O Iblias	O Idelvion
O Immunine O NovoEight O Other:	O Kogenate O Nuwiq O Unknown	O Kovaltry O Octanate			O Nonafact O Rixubis
O Factor IX products					
O Alprolix O Rixubis	O BenefIX O Other:	O Idelvion O Unknown	O Immunine	O Mononine	O Nonafact
O Bypassing agents: O FEIBA O Unknown	O rFVIIa	O Other:	O Unknown		
Note additional infor for selected product:		O Dose:		Ο IU/kg Ο μg/kg Ο U	Ο U/kg Ο IU Ο μg
		O Unknown		O Other:	

2.4.3 Treatment of a life threatening bleed?

O Factor VIII products					
O Aafact	O Advate	O Adynovate	O Afstyla	O Alprolix	O BeneFIX
O Elocta	O Haemate P	O Helixate Ne	xGen	O Iblias	O Idelvion
O Immunine	O Kogenate	O Kovaltry	O Mononine	O Nanotiv	O Nonafact
O NovoEight	O Nuwiq	O Octanate	O Refacto AF	FuseNGo	O Rixubis
O Other:	O Unknown				
O Factor IX products					
O Alprolix	O BenefIX	O Idelvion	O Immunine	O Mononine	O Nonafact
O Rixubis	O Other:	O Unknown			
O Bypassing agents:					
O FEIBA	O rFVIIa	O Other:	O Unknown		
O Unknown					
				_	
Note additional infor		O Dose:		O IU/kg	O U/kg
for selected product:				Ο μg/kg	O IU
				ΟU	Ο μg
				O Other:	
		O Unknown			

3.0 Inhibitor Development (haemophilia A patients only)

3.1 Currently or previously positi Bethesda assay	ve O No (proceed to chapter 4. O Unknown (proceed to cha O Yes, (proceed with followi	pter 4.0)	
3.2 Currently undergoing immun tolerance induction (ITI)?	e O No (continue with 3.4) O Yes (continue below)		
3.2.1 Product used (select only or	ne product):		
O Immunine O Kogenate O NovoEight O Nuwiq O Other: O Unknown O Factor IX products O Alprolix O BenefIX	P O Helixate NexGen e O Kovaltry O Mononine O Octanate O Refacto AF	O Iblias O Nanotiv	O Rixubis
3.2.2 Note additional information for this product:	O Starting date: Dose: IU/kg Frequency: times per O Unknown		O 1 week
3.3 Use of immunosuppressants at any time point during ITI?	O No O Yes, continue below, mult	iple choice)	
 Rituximab intravenous immunoglobulin Mycophenolate mofetil Methotrexate Hydrocortisone 	 Immunoadsorption Cyclophosphamide Azathioprine Dexamethasone Other: 		

3.3.1 If yes, note additional				
information per product:	O Used from:	dd/mm/	'yyyy to:	_dd/mm/yyyy
)
	Frequency:	_ times per	O day	O 2 days
			•	O 1 week
			O 2 weeks	O Other:
	O Unknown			
3.4 First positive Bethesda a	ssav (according to local	cut-off)		
Date	0:	-		
	O Unknown	,, , , , ,		
Inhibitor titre	0:	BU/mL		
	O Unknown	,		
Recovery FVIII:C	0:	IU/mL. afte	er a bolus of	IU/kg FVIII
	O Unknown	_ 10,112, area		
Cumulative N of	0:	exposure da	vs (at inhihito	or detection)
exposure days	O Unknown		ys (at minore	accellony
3.5 Second positive Bethesd				
Date	0:	dd/mm/yy		
	O Unknown			
Inhibitor titre	O: BU/mL			
	O Unknown			
Recovery FVIII:C	O: IU/mL, aft		er a bolus of_	IU/kg FVIII
	O Unknown) Unknown		
3.6 Highest inhibitor titre ev	er measured			
Date		dd/mm/w		
Date	O Unknown	dd/mm/yy		
Inhibitor titre	0:	BU/mL		
	OO Unknown	_ DO/IIIE		
Recovery FVIII:C	0:	III/mL afte	or a bolus of	
Recovery FVIII.C	0 O Unknown			10/kg1 VIII
	O UTKITOWIT			
3.7 Initiation of immune tole	erance induction (ITI)			
ITI initiated	O no O yes O unknowr	า		
Date	(
2.9 First possible Dathasda				
3.8 First negative Bethesda a Achieved				
	O no O yes O unknowr			
Date	(ий/ ППП/ уу		
3.9 First normal recovery				
Achieved	O no O yes O unknowr	า		
Date	(dd/mm/yy		

3.10 Confirmed inhibitor re	lapse	
after a successful		
ITI-procedure?	O No	(proceed to chapter 4.0)
	O Unknown	(proceed to chapter 4.0)
	O Yes	(proceed with following questions)
3.11 First positive Bethesc	la assay (accord	ing to local standards) after successful ITI
Date		dd/mm/yy
	O Unknown	
Inhibitor titre	0:	BU/mL
	O Unknown	
Recovery FVIII:C	0:	IU/mL, after a bolus of IU/kg FVIII
	O Unknown	
Cumulative N of	0:	exposure days (at inhibitor detection)
exposure days	O Unknown	
3.12 Second positive Beth	esda assay after	successful ITI
Date	=	dd/mm/yy
	O Unknown	
Inhibitor titre	0:	BU/mL
	O Unknown	
Recovery FVIII:C	0:	IU/mL, after a bolus of IU/kg FVIII
	O Unknown	
3.13 Highest inhibitor titre	e ever measured	after successful ITI
Date		dd/mm/yy
	O Unknown	
Inhibitor titre	0:	BU/mL
	O Unknown	
Recovery FVIII:C	0:	IU/mL, after a bolus ofIU/kg FVIII
	O Unknown	
3.14 Initiation of immune	tolerance induc	tion (ITI) after inhibitor relapse
ITI initiated	O no O yes O	
Date		
3.15 First negative inhibito	or test after inhi	bitor relapse
Achieved	O no O yes O	unknown
Date		dd/mm/yy
3.16 First normal recovery	after inhibitor	relapse
Achieved	O no O yes O	-
Date		dd/mm/yy

4	l.0 Co-morbidities	
4.1 Currently HIV positive?	O no (continue with 4.2)	
	O yes (fill in below)	
	Treatment regimen:	
	HIV viral load (last HIV RNA assay):	copies/mL
4.2 Currently or previously positive for hepatitis C?	O no (end of CRF)	
	O yes (continue below)	
	HCV genotype (including subtype):	0 1a 0 1b 0 2a 0 2b 0 Other: 0 Unknown
	Date of last positive HCV RNA assay:	dd/mm/yyyy
	Outcome of last Fibroscan:	kilopascal (kPa)
	Last recorded Child-Pugh score:	O Unknown O class A O class B O class C
	Presence of ascites:	O Yes O Unknown
	Presence of bleeding oesophageal varices :	O Yes O Unknown
	Presence of hepatic encephalopathy:	O yes O unknown
	Liver transplantation:	O yes O unknown

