5.1.3 Electronic patient records

The clinical data will be collected from the medical charts using a case report form. Each patient will be assigned a unique study code, as described in chapter 8. A copy of the CRF will be sent to the coordinating centre (Leiden University Medical Centre) for data entry and a copy will be kept at the original centre. We will obtain the following information from electronic patient records, along with the dates at which measurements were performed:

• Variables that will be extracted from the electronic patient records:

General

- Year of birth
- Vital status, if deceased:
 - Cause of death
- Type of haemophilia
- Bodyweight and height
- Age at first joint bleed
- F8 or F9 genotype
- Date of first blood sample
- Date of last FVIII/FIX infusion before first blood sample
- Product and dose used during last FVIII/FIX infusion before first blood sample
- Baseline FVIII/FIX activity level (one-stage clotting assay/chromogenic assay)
- Baseline FVIII/FIX antigen level
- Baseline VWF activity level, baseline VWF antigen level (VWF: Ag)
- Current treatment type (prophylactic treatment or on-demand treatment) , frequency and dose
- Bodyweight and height

Current treatment

- Current treatment regimen
 - Current product(s) used
 - Prophylaxis vs. on-demand treatment

- Frequency, dose of prophylactic treatment (if applicable)
- Frequency, dose of treatment for minor/major/life-threatening bleeding
- Immune tolerance induction protocol (if applicable)
 - Current product(s) used
 - Frequency, dose
 - o Use of immune modulatory medication

Co-morbidities

- HIV status, if positive:
 - o Treatment type
 - HIV viral load
- Current and previous hepatitis C status, if positive:
 - HCV genotype
 - o Date of last positive HCV RNA assay
 - Outcome of last Fibroscan
 - Latest Child-Pugh score
 - o Presence of ascites
 - Presence of bleeding oesophageal varices
 - Presence of hepatic encephalopathy
 - Liver transplantation
 - o All previous HCV treatment regiments
 - o SVR after last HCV treatment

Inhibitor development

- Number of exposure days to FVIII (<50 EDs, 51-100 EDs, 101-150 EDs, >150 EDs)
- Previous or current Bethesda assay, if positive:
 - o Number of exposure days to FVIII before first positive inhibitor assay
 - First two positive inhibitor assays (date, inhibitor titre and FVIII:C recovery)
 - o Peak inhibitor titre and corresponding FVIII:C recovery
 - o Initiation of immune tolerance induction (ITI)

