6.1 Studies describing the health status of the Dutch haemophilia population

6.1.1 45 years of haemophilia treatment in the Netherlands, 1972-2017

Primary objective 1: To describe changes in bleeding, factor consumption, self-reported bleedinginduced joint damage, inhibitor formation, HIV/HCV infection as well as cause-specific and all-cause mortality among Dutch PWH for the period 1972-2017.

Study design and population: We will compare between HiN-study cohorts (previous and current) on the endpoints stated below. For mortality, we will also compare our data to that of the general male population. The population will consist of all previous HiN-study cohorts as well as the current HiN-6 cohort.

Determinant: Disease severity and calendar time

Endpoints: Self-reported annual joint bleed rate/factor consumption, self-reported bleeding-induced joint disease, inhibitor formation, HIV/HCV infection, all-cause/cause-specific mortality will be used as endpoints. Information on these endpoints will be obtained using a questionnaire. **Statistical analysis:** We will use descriptive statistics where appropriate.

Primary objective 2: To describe the prevalence of several haemophilia-related and nonhaemophilia related co-morbidities in the Dutch haemophilia population and to compare these results with the general Dutch male population.

Study design and population: A cross-sectional study design will be used. The population will consist of all PWH in the Netherlands.

Determinant: Disease severity, HIV/HCV infection status and inhibitor status.

Endpoints: Cardiovascular disease (CVD), malignancies, obesity, liver disease, chronic kidney disease (CKD), diabetes, osteoporosis, chronic pain and mental health. Information on these endpoints will be collected using a questionnaire and/or from each patient's medical record.

Statistical analysis: We will use descriptive statistics, standardized by age. Our results will be compared with national figures for the general male population provided by the Central Bureau of Statistics Netherlands StatLine databank, standardized directly or indirectly by age.

HiN-6 study

Primary objective 3: To describe the uptake, efficacy and safety of hepatitis C treatment in PWH currently or previously infected with hepatitis C.

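### Four liver-complication items in CRF item 4.2 have no No option, so among patients ever HCV positive, documented absence is mixed with missing documentation

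*Protocol*

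**What the plan says.** Protocol section 5.1.3 lists variables to be taken from the patient record. For patients with current or past hepatitis C these include "Presence of ascites", bleeding varices, "Presence of hepatic encephalopathy" and liver transplantation.

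Appendix 1, section 4.0, item 4.2 turns these into form fields. Encephalopathy and transplantation read "O yes O unknown". Ascites and varices carry the same two options with capital initials. None of the four shows a No box.

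The same block holds two other measures of liver status. One is Child-Pugh class, with options "O Unknown O class A O class B O class C". The other is a stiffness value in kPa, "Outcome of last Fibroscan". The block is reached only by patients who are or were HCV positive; for everyone else the form ends there.

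Liver data serve section 6.1.1, primary objective 2, whose endpoints are "Cardiovascular disease (CVD), malignancies, obesity, liver disease, chronic kidney disease (CKD), diabetes, osteoporosis, chronic pain and mental health". They are described in all persons with haemophilia, from the questionnaire, the medical record or both.

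**The concern.** A yes/no chart item needs three answers: present, absent, and not documented. Without the second, a patient examined and found free of ascites gets the same entry as a patient whose chart is silent, or a blank that cannot be told from a skipped item. Analysis cannot separate the two groups later, because the distinction was never recorded. A second look at the charts would be needed.

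At stake is the prevalence of four separately collected complications in the HCV-ever subgroup, within a study that gives viral infection special focus.

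**Working it through.** The protocol gives no figure to reproduce. The check compares the form's items with each other and then works out what can be estimated from the four.

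**1. Is Yes/Unknown the form's convention?** No.
- Items 1.12 to 1.14 (additional bleeding disorders), 2.3 (prophylaxis), 3.10 (inhibitor relapse), 4.1 (HIV) and 4.4 (sustained response) all offer No.
- Items 3.7 to 3.9 offer all three answers. Item 3.9 reads "O no O yes O unknowr", where the last letter is a reading error.
- One exception was found: the follow-up question in 1.10 on whether another von Willebrand activity assay was used also shows only Yes and Unknown.

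**2. Does an instruction fill the gap?** No. For section 4.0 the instruction sheet comments only on item 4.4. Section 8.2 says that data are checked for missing values, so a blank is more likely to be queried than read as absence.

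**3. What can be estimated?** Let n be the number of HCV-ever patients, y those marked Yes, and u those whose chart is silent. As the form stands, n − y patients are Unknown or blank, and u cannot be identified within them.
- Lower bound: y/n, which treats every non-Yes patient as free of the complication.
- Upper bound: 100%, because nothing on the form excludes any non-Yes patient.
- With a No box the bounds become y/n and (y + u)/n, and the proportion among documented patients is y/(n − u).

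**4. Illustration.** The counts are assumed and not from the protocol: n = 100, y = 8, documented absent = 72, u = 20.

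| Quantity | Form as it stands | With a No box |
|---|---|---|
| Lower bound | 8/100 = 8% | 8/100 = 8% |
| Upper bound | 100% | (8 + 20)/100 = 28% |
| Proportion among documented patients | not available | 8/80 = 10% |

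The lower bound falls short of the documented-patient figure by (10 − 8)/10 = 20%. In general y/n = [y/(n − u)] × (1 − u/n); here 10% × (1 − 0.20) = 8%. The relative shortfall therefore equals the undocumented share u/n, which the form does not measure.

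**The case against.** The strongest objection is that the missing box may be an extraction fault. The text was read from a PDF, and options are visibly lost nearby. Items 3.14 and 3.16 have lost Unknown. In item 4.3, ribavirin is missing from three of the six treatment blocks and interferon from one. The four rows are adjacent, so one fault could affect them all. This cannot be excluded, and the original form must be checked first. It is still the less likely explanation. The nearby losses are irregular and mostly leave gaps, whereas here only No would have vanished, cleanly, from four consecutive rows in two letter-case styles, while the Child-Pugh row kept every class.

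A second objection is that blanks can be told from a ticked Unknown, and a copy of each form stays at the centre, so records can be queried. That is true, but it helps only if every centre leaves a blank for absence and ticks Unknown for silence. No instruction asks for this, and going back to the charts is the extra work that a No box avoids.

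A third is that Yes over all HCV-ever patients is usable. It is, as a lower bound, and it should be labelled as one.

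A reader might also infer that advanced liver disease, or the liver disease endpoint, cannot be estimated, or that the form yields 100% prevalence. The protocol does not support this. It defines no endpoint called advanced liver disease. The named endpoint covers all persons with haemophilia and also draws on the questionnaire, which has blocks on hepatitis C and on other conditions. Child-Pugh class and Fibroscan are recorded independently of the four items. A figure of 100% arises as an estimate only if Yes is divided by Yes, which no section plans. In the working above it is an upper bound.

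**Conclusion.** The point holds in a limited form. For ascites, bleeding varices, encephalopathy and liver transplantation, the form as extracted merges patients known to be free of the complication with patients whose chart is silent. Their prevalence among HCV-ever patients is then available only as a lower bound or under an unstated assumption. The relative shortfall of that bound against the documented-patient figure equals the undocumented share: 20% if one chart in five is silent, which is an assumed value.

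The damage is confined to four descriptive variables in one subgroup. Child-Pugh class and stiffness do not replace them, since neither shows which complication occurred, but they keep the wider liver disease endpoint estimable. The conclusion rests on the original form matching the extracted text. It is a small defect, worth correcting because correction is nearly free before data collection.

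**What to change.** First confirm on the original form that the four items have no No option. If so:

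- Add No to the four items in CRF item 4.2.
- Add one line to the instruction sheet for item 4.2: Unknown means not documented in the record, and the items are not to be left blank.
- Report Yes/(Yes + No) for each complication together with the share Unknown. The share is needed because a complication may be charted more reliably than its absence, in which case the proportion among documented patients would be too high.

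The cost is four tick boxes and one sentence before data collection. If forms have already been completed, HCV-ever patients marked Unknown or left blank on these items would need a second chart check; otherwise the results should be presented as lower bounds.
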